Primary Specific Aim 2: Test the impact of dementia screening on the mood and anxiety symptoms of patient at baseline and 1, 6, and 12 months (i.e., primary potential harms).

(We hypothesize that screened subjects will not have higher depression or anxiety at one month post-screening (as measured by the Patient Health Questionnaire (PHQ-9) and Generalized Anxiety Disorder (GAD-7) scales)

Secondary Aims: Estimate the cost effectiveness of dementia screening.

(We hypothesize that screened subjects will have an Incremental Cost Effectiveness Ratio (ICER) below the maximum acceptable threshold of \$100,000 per quality adjusted life year saved at 12 months.)

B. Innovation

Pragmatic

Previous studies by our team and others have demonstrated that routine feedback of dementia screening scores, continuing medical education for dementia, and other passive educational interventions can improve rates of diagnosis, but not patient outcomes.^{12,28-32} We have shown that patients and families perceive potential harms from screening and that dementia screening can result in important incremental health care costs.^{21-23,33} Conversely, we and others have also already demonstrated that collaborative care, focused on non-

pharmacologic approaches to behavioral disturbances, can improve patient outcomes under experimental conditions.^{34,35} The innovation of this trial is in moving the process upstream to asymptomatic, older adults, cared for in typical but prepared community-based practices, to document actual benefits and harms, including costs. “Asymptomatic”, in the case of cognitive impairment, is paradoxical in some respects, but we denote asymptomatic to mean that the cognitive impairment is not a presenting symptom of the patient (just as hypertension is asymptomatic but can be detected by screening, cognitive impairment can be detected through screening tests).

Academic Community Partnership

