had positive attitudes of dementia screening such as that 65% to 90% felt that dementia screening would provide them with the opportunity to plan their future finance and health care, advance directive, to participate in research, and motivate them to have a healthier life style. Few older adults perceived a negative impact of dementia screening on their emotional health or their independence. These findings suggest that the process of dementia screening may improve the quality of life not only for patients with unrecognized dementia but also for older adults with screen negative results, including at minimum the assurance of the absence of significant cognitive impairment. However, older adults did report concerns about potential harms including suffering from depression or anxiety, loss of driving privileges, difficulty obtaining long-term health insurance, and worries that people would treat them differently.²¹⁻

23,100

Estimating Economic Impact

To investigate the current and future economic impact of the collaborative dementia care management program in primary care settings, we developed a model to evaluate the net benefits for CMS of applying the collaborative dementia care program early via a routine screening in primary care. We used data from the collaborative dementia care trial, the dementia screening and diagnosis study, the USPSTF systematic review, and North Carolina public health impact of dementia forecasting study.^{1,33,34,79} We used cost terminology suggested by Gold et al.¹⁰¹ Direct formal costs included those costs in which a Medicare payment will be made for the services (e.g., physician visits, medications, hospital care, paid home care, and long-term care services); direct informal costs were the hourly wage of a worker who would need to be hired to provide the same care that an unpaid caregiver is providing; and finally cost estimates for different time periods were inflated by the Medical Care component of the Consumer Price Index (CPI). After estimating the per capita total annual costs, we generated aggregate estimates of dementia prevalence over the period 2010 - 2050. The per-patient costs

were multiplied by the national prevalence weight to extrapolate the sample costs to population size for calculation of the total direct aggregated healthcare cost.

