Statistical Power, derived from sample size estimate, is used to test the primary hypothesis that subjects in the screening group will have higher health related quality of life than the no screening group. Previous randomized trials comparing collaborative care to usual care in demented patients have stated effect size of 0.4 being clinically significant.^{34,35} Considering that the majority of patients in the screening group or the no screening group are not demented, the observable effect size between these two groups will be a combined effect size measure in the non-demented subjects and in those demented subjects receiving the collaborative dementia care program.

Assuming 85% sensitivity of screening instrument and 15% prevalence of dementia in this patient population, to achieve 80% power to detect a significance effect size of 0.094 between the screening group and the no screening group at $\alpha=0.05$ level (two-sided), and allowing 10% of patients with missing follow-up outcomes at 12 months, we need to enroll at least 3951 patients into the study. The effect size of 0.094 between the screening group and the no screening group reflects a difference of 0.40 SD between demented patients in the collaborative dementia care program and demented patients who were not screened and a difference of 0.06 SD in the majority of patients who are not demented in either group. We demonstrate in the table below that our planned sample size of 4,000 will have sufficient power to detect significant differences between the “screen” group and the “no screen” group under various scenarios assuming varying degrees of efficacy measures for the collaborative dementia care program and for the screening only subjects.

Estimated power with a total sample size of 4,000 comparing primary outcome measures between the screening group and the no screening group (two-sided at $\alpha=0.05$) allowing 10% of patients with missing outcomes at 12 months.			
Effect size of collaborative care in demented subjects	Effect size In non-demented subjects	Observable Effect Size	Power Estimate
0.3	0.07	0.091	77.9
	0.08	0.100	85.1
0.4	0.07	0.102	86.4
	0.08	0.110	91.0

For the Secondary Aims, given the sample size of 4000, we will have greater than 95% power to test the equivalence levels in PHQ-9 and GAD-7 at 1 month assuming equivalence differences of 0.6 (SD=5.1) on PHQ-9 and 0.5 (SD=3.2) on GAD-7 based on our previous studies in primary care patients.^{34,51,93,114-118}

J. Limitations

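### The one-month no-harm hypothesis is one-sided but is powered as equivalence, and the analysis section gives no margin or decision rule for it

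*Combined protocol and SAP*

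**What the plan says.** The hypothesis under Primary Specific Aim 2 has a direction: "We hypothesize that screened subjects will not have higher depression or anxiety at one month post-screening". The instruments are the PHQ-9 and GAD-7, and the aim describes these outcomes as the main potential harms.

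In section I, Statistical Plan, the same comparison appears as Secondary Aim 1. The planned analysis is ANCOVA of the one-month scores, adjusted for baseline scores and patient characteristics. No margin, significance level, confidence-interval rule or type of test is given there.

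The end of the power discussion in section I is the only place that names a test. It puts the figure above 95% and describes it as "power to test the equivalence levels in PHQ-9 and GAD-7 at 1 month assuming equivalence differences of 0.6 (SD=5.1) on PHQ-9". For GAD-7 the corresponding margin is 0.5 points, with an SD of 3.2. The paragraph states no significance level, sidedness, assumed true difference or allowance for missing one-month data.

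**The concern.** Equivalence in its usual sense has two bounds: scores in the screened group must be neither higher nor lower by more than the margin. Only the upper bound bears on harm. The lower bound adds a condition that the stated hypothesis does not contain, and a real improvement in mood makes that condition harder to meet.

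Because the analysis paragraph has no rule, the analyst must choose one later. The only guide is the word equivalence, which does not match the hypothesis. For some results that choice decides whether the trial declares no harm, on outcomes that the protocol treats as the main potential harms of screening.

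**Working it through.** **Inputs.** Margins m and SDs from the power paragraph: PHQ-9 0.6 and 5.1; GAD-7 0.5 and 3.2. Allocation is 1:1, so 4,000 gives n = 2,000 per arm. The plan's 10% missing is stated for 12 months only; it is borrowed here as a sensitivity case (n = 1,800). Let d be the true difference, screening minus no screening, so a negative d is an improvement.

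**Formulas** (normal approximation). SE = SD × √(2/n).
- Equivalence: Φ((m − d)/SE − z) + Φ((m + d)/SE − z) − 1.
- Non-inferiority: Φ((m − d)/SE − z).
- z = 1.645 for 5% per side, 1.960 for 2.5%.

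**The plan's own figure.** With d = 0 and n = 2,000:
- PHQ-9: SE = 0.1613, m/SE = 3.720, Φ(3.720 − 1.645) = 0.9810, so equivalence power is 2 × 0.9810 − 1 = 96.2%.
- GAD-7: SE = 0.1012, m/SE = 4.941, Φ(3.296) = 0.9995, power 99.9%.

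The claim of more than 95% therefore reproduces with 5% per side. With n = 1,800, PHQ-9 falls to 94.1% and GAD-7 to 99.8%. With 2.5% per side, PHQ-9 gives 92.2% at n = 2,000, which would not reproduce. One-sided non-inferiority at 2.5% gives Φ(3.720 − 1.960) = 96.1% on PHQ-9, so the stated figure cannot show which test was meant.

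**If mood improves.** The sizes 0.06 and 0.094 SD are the plan's 12-month quality-of-life assumptions, used here only as a scale; 0.03 SD is half the smaller one. Example for PHQ-9 at 0.06 SD: d = −0.306, (0.6 − 0.306)/0.1613 = 1.823, Φ(1.823 − 1.645) = 57.1%; the other term is practically 1. Ranges run from n = 1,800 to n = 2,000, at 5% per side.

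| True improvement | PHQ-9 points | PHQ-9 equivalence | GAD-7 points | GAD-7 equivalence | Non-inferiority, 5%, both scales |
|---|---|---|---|---|---|
| 0.03 SD | 0.153 | 83.5–86.9% | 0.096 | 98.4–99.1% | at least 99.7% |
| 0.06 SD | 0.306 | 53.4–57.1% | 0.192 | 89.3–91.9% | over 99.9% |
| 0.094 SD | 0.479 | 17.5–18.5% | 0.301 | 58.8–62.7% | over 99.9% |

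All these true differences lie inside the margins. Equivalence fails because the confidence interval crosses the lower bound: if the observed PHQ-9 difference were −0.479, the lower 90% limit would be −0.479 − 1.645 × 0.1613 = −0.745.

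**Baseline adjustment.** ANCOVA multiplies the SD by √(1 − ρ²). With ρ assumed at 0.5 to 0.7 and n = 2,000, success at 0.094 SD becomes 22–27% on PHQ-9 and 73–87% on GAD-7. Adjustment helps, but does not remove the effect on PHQ-9.

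**Power under the proposed rule** (one-sided 2.5%, d = 0, unadjusted SD): PHQ-9 96.1% and GAD-7 99.9% with 2,000 per arm; 94.2% and 99.7% with 1,800.

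**The case against.** The strongest reply is that no equivalence test is planned. The analysis paragraph specifies only ANCOVA, and equivalence may be loose wording for non-inferiority. An ANCOVA estimate with its upper confidence limit would show absence of harm whatever the lower limit. This stands: the mismatch lies in the power statement, and the more basic gap is the missing rule.

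A second reply is that the improvement is hypothetical. This also stands. The documents assume no effect on mood. The assumption of "a difference of 0.06 SD in the majority of patients who are not demented in either group" concerns quality of life at 12 months, and the 0.094 SD figure includes a 0.40 SD effect in patients with dementia receiving collaborative care. Little of that care can have acted by one month, since section E puts the second home visit two to four weeks after the first. Section D does expect screening to help screen-negative people, "including at minimum the assurance of the absence of significant cognitive impairment", but it speaks of quality of life and goes on to report worries about depression and anxiety. Section L limits what is disclosed at the initial screen, so reassurance by one month is not routine.

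A third reply is that the aim itself, as distinct from its hypothesis, is worded as a test of impact in either direction. That is so, but a two-sided estimate with its interval serves that aim; a lower equivalence bound is not needed for it.

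A reader might go further and infer that a mood benefit would make the trial's no-harm test fail. The documents do not support that. No such test is laid down, and among the four combinations of scale with 0.06 or 0.094 SD, failure is the usual result in only one: PHQ-9 at 0.094 SD. PHQ-9 at 0.06 SD passes slightly more often than not, and GAD-7 passes more often than not at both sizes.

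**Conclusion.** The point holds as a mismatch with a missing rule. The hypothesis is one-sided, the only named framing is equivalence, and nothing in the analysis paragraph settles how no harm will be judged. The stated power is not wrong: it reproduces for zero true difference and complete one-month data, and falls just short on PHQ-9 (94.1%) with 10% missing and no gain from baseline adjustment.

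The size of the consequence depends on an improvement that the documents do not assume. Across 0.03 to 0.094 SD, equivalence success on PHQ-9 runs from about 87% down to about 18%, with a milder fall on GAD-7. Non-inferiority is almost unaffected. These figures rest on the normal approximation, the plan's SDs and 5% per side. The change is worth making because it ties the rule to the hypothesis at almost no cost.

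**What to change.** In the power paragraph of section I, replace equivalence with one-sided non-inferiority at the margins already given. In the Secondary Aim 1 paragraph, add the rule: no harm is concluded if the upper limit of the two-sided 95% confidence interval (one-sided 2.5%) for the ANCOVA-adjusted difference, screening minus no screening, is below +0.6 on PHQ-9 and below +0.5 on GAD-7. No lower bound applies.

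Restate power at zero difference as 96.1% (PHQ-9) and 99.9% (GAD-7) with 2,000 per arm, or 94.2% and 99.7% with 10% missing. Because both scales must pass, joint power is at least 96.08 + 99.86 − 100 = 95.9% with 2,000 per arm, whatever the correlation between them.

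The change needs no further patients, visits or data. The trial gives up a formal claim that screening does not improve mood, and must accept a PHQ-9 power slightly below 95%, before any gain from baseline adjustment, if 10% of one-month scores are missing.

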The director of the clinical core ([name]) will meet with the Advanced Practice Nurse on a weekly basis to review the performance of the program, its fidelity and any complicated care using the electronic reports generated by the care coordination support software (eMR-ABC). The eMR-ABC will provide [name] with a weekly report of the performance of the care coordinator in regards to the adherence of delivering specific protocols.

The Usual Care Control Groups:

The 2,000 subjects who would be randomized into the “no screening group” will continue to receive their usual care, including a referral to the local memory care practices if their primary care provider suspects the presence of a cognitive problem at any time during the study follow-up.

Overview of Data Sources		
Construct	Source of data	Specific variables/Instruments
Social, Demographic, Advance care planning	Study Survey	MOS, age, gender, race, education, income, living situation, marital status, and advance care planning
Health Related Quality of Life, Mood and Anxiety	Study Survey	HUI, PHQ-9, GAD-7
Health Care Utilization	Indiana Network for Patient Care records for the 4000 subjects	ER episode, location
		Hospital episode, location
		Inpatient diagnoses (ICD9 codes)
		Length of stay
Co-morbidity	Indiana Network for Patient Care records for the 4000 subjects	ICD-9 codes for the 10 common chronic diseases

Medication Use	Indiana Network for Patient Care records for the 4000 subjects	Psychotropics
Care Processes	eMR-ABC and INPC	Visits to memory care practice. Collaborative dementia care team visit. Visits with HABC monitor Protocols delivered by the care team

F. Inclusion/Exclusion Criteria

Inclusion criteria include:

- adults age 65 and older;
- at least one office visit to their primary care physician within the previous year;
- no previous diagnosis of dementia or memory problem as determined by ICD-9 codes or the presence of prescription for anti-dementia medications (cholinesterase inhibitors or memantine);
- ability to consent to participate in the study; and
- ability to communicate in English

[figure not shown]
Exclusion criteria include:

- adults who are a permanent resident of a nursing facility;
- a serious mental illness such as bipolar disorder or schizophrenia as determined by the presence of related ICD-9 codes indicative of such an illness; or
- a pre-existing diagnosis of dementia or cognitive impairment

G. Enrollment/Randomization

Clinical Settings and Population

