Recruitment and informed consent: Our proposal will be approved by the Indiana University-Purdue University Indianapolis Institutional Review Board and the primary health centers where

the patients receive their care. Our study will require having informed consent from patients. The consent will be for the subject's involvement in the process of collecting data from HUI, PHQ-9, GAD-7, the MOS social support questionnaire, administrative data extraction in a de-identified manner and the possibility of undergoing dementia screening process if the subject is randomized into the screening arm of the study.

Consent procedure protection against risk: This study utilizes in person methods of recruitment and consent. Persons who are hearing impaired or too ill to answer questions will not be asked to participate in an interview. Subjects will not be asked to continue with the recruitment and enrollment processes who cannot understand the questions being asked of them, as indicated by either continued non-responsive answers or by asking the interviewer to repeat more than three questions three times each. In addition, we have employed usual methods of determining capacity to consent by asking the subject to repeat in their own words a description of the study and their rights as a research subject. Because we are recruiting only individuals without a diagnosis of dementia or some other form of diagnosed cognitive impairment, we have further limited the risk of soliciting from individuals who lack capacity, even though we recognize up to 6% of the sample may meet criteria for a dementia condition.

Moreover, should some individuals have mild to moderate dementia, we have evidence from prior studies that demonstrate that such individuals often have decision-making capacity and are able to recognize the risk-benefit profiles of various research study scenarios.^{127,128} Patients who refuse to participate in the study will not be approached again. The format and the procedure of data collection will be outlined in the consent form, the data will be extracted into a pre-designed database, and the research assistant will not collect any additional data without the consent of the patient and the university IRB. This process of approach and consent will adhere to all usual human subjects' policies and procedures. We will use the standard

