procedures for addressing capacity that are employed by many institutions' human subjects review boards. The following questions will be employed:

I just went over what participating in this study entails. I am going to ask you a few questions just to make sure you understand the study before we begin.

1. What would you be doing if you agree to participate in this study?
(Examples of acceptable answers: "Take part in an interview/survey," or "Answer questions about my friend or relative.")
 Person is able to answer this Person is **not** able to answer this

2. What can you do or ask me to do if you are uncomfortable with a particular question in the survey?
(Examples of acceptable answers: "Ask to skip the question." "Ask you to read another question.")
 Person is able to answer this Person is **not** able to answer this

3. What can you do if you decide after we start that you do not want to participate in the study?
(Examples of acceptable answers: "Tell you that I do not want to answer any more questions.")
 Person is able to answer this Person is **not** able to answer this

For initial screening results, diagnostic determination will not be provided at that time except in instances where the subject asks and the results are considered normal. The interviewer will have a scripted response that indicates the test is not diagnostic and the results will be provided to the primary care provider (if the patient and/or proxy agree). They will be instructed that this can be discussed with that primary care provider.

For those subjects who screen positive and are determined to meet criteria for dementia, the team will disclose the finding of new information about the patient's health status (using carefully scripted protocols mindful of the potential harm that may result from disclosure of a stigmatizing condition) directly to the patient and the primary care physician. The principal investigator will be available to clarify any questions and offer any needed consultation.

We make the distinction between research-obtained data (through in-person and telephone interviews and electronically extracted data) and clinical data (obtained through

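### The capacity script accepts an answer that does not fit this trial, and its listed answers can be given without any sign of knowing that dementia screening may follow

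*Combined protocol and SAP*

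**What the plan says.** Section F (Inclusion/Exclusion Criteria) requires "ability to consent to participate in the study". Section L, under the consent procedure, describes how capacity is judged: the subject is asked to "repeat in their own words a description of the study and their rights as a research subject". The section then sets out three questions to be used, each with a box for able or not able.

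- Question 1: "What would you be doing if you agree to participate in this study". Acceptable examples: "Take part in an interview/survey" or "Answer questions about my friend or relative".
- Question 2: "What can you do or ask me to do if you are uncomfortable with a particular question in the survey". The examples concern skipping or changing a question.
- Question 3 asks what the person can do on deciding to stop. The example is telling the interviewer so.

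The recruitment and consent paragraph of section L says that consent covers the subject's own questionnaires (HUI, PHQ-9, GAD-7, MOS social support), data extraction, and "the possibility of undergoing dementia screening process if the subject is randomized into the screening arm of the study". Under potential risks, section L says that screening or the later assessment may lead to a dementia diagnosis, with possible discrimination, loss of independence or psychological burden.

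**The concern.** A capacity check is only as good as its scoring standard. Here one of the two listed answers to the key question describes an informant study, which this is not. An interviewer following the form would mark as able a person who believes the study is about someone else.

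The other listed answer is correct but generic. It would fit almost any questionnaire study and shows nothing about the feature that sets this one apart: a chance of being tested for dementia, with a possible diagnosis to follow. The design makes that reply a natural one, because the cognitive screener sits inside a broader set of health questions (section E, Screening Process).

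What is at stake is the validity of consent, and the correct use of an eligibility criterion, in a sample that the protocol expects to include people with undiagnosed dementia.

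**Working it through.** The point rests on the text, so the check compares the script with what the study asks of people.

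**Step 1: whose data are collected?** The Overview of Data Sources table and section H (Data Collection) list the subject's own HUI, PHQ-9, GAD-7, social support, demographics and advance care planning, plus the subject's own records. No study survey asks the subject about a friend or relative. Caregiver input appears in the collaborative care program, which follows a positive screen and referral, and in the economic evaluation. In the program it is the caregiver, not the enrolled patient, who completes the HABC Monitor. The friend-or-relative answer therefore describes nothing that an enrollee does.

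**Step 2: can the script be passed without awareness of screening?**

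| Element of the study | Q1 listed answers | Q2 | Q3 |
|---|---|---|---|
| Answering questions about oneself | Not required; one answer contradicts it | No | No |
| Possible dementia screening | No | No | No |
| Allocation by chance | No | No | No |
| Possible diagnosis after a low score | No | No | No |
| Right to skip an item | No | Yes | No |
| Right to stop | No | No | Yes |

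A person can give a listed answer to all three questions and never touch rows two to four. No rule states how many of the three must be answered acceptably.

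**Step 3: does the teach-back close the gap?** It asks for a description of the study in the subject's own words but does not say what that description must contain. The only scoring standard given is the set of example answers in the script.

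**Step 4: is the script tied to consent by telephone?** The consent procedure in section L says that recruitment and consent are in person. Telephone Recruitment in section E adds consent by telephone. The protocol does not say whether the same script is used there.

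**Step 5: scale.** The plan gives no figure for misunderstanding, so there is none to reproduce. The expected number with dementia can be calculated from the protocol's own two rates:

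- Section L, up to 6%: 0.06 × 4,000 = 240 enrolled, and 0.06 × 2,000 = 120 in the screening arm.
- Section I (Statistical Plan), 15% assumed for power: 0.15 × 4,000 = 600 enrolled, and 0.15 × 2,000 = 300 in the screening arm.

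These numbers describe the population in which the check matters most. They do not count people who would pass it wrongly.

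**The case against.** The best defence is that the script does not stand alone. Section L also stops recruitment of anyone who gives continued non-responsive answers or needs more than three questions repeated three times each. It provides the teach-back and does not recruit people with diagnosed dementia or cognitive impairment. Section E has the treating clinicians authorise the approach and asks patients to sign informed consent. All of this stands. A reader might infer that the script is the only protection at enrolment, and the protocol shows that it is not.

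It can also be said that the answers are labelled as examples, that question 1 is open, and that the script begins after the study has been explained. This is fair as far as it goes. A subject may mention screening unprompted, and the consent is stated to cover it. Consent pages are not in the review copy, so nothing can be concluded about what subjects are told. The point concerns what is tested, not what is disclosed. Calling the answers examples does not rescue the friend-or-relative answer, which is expressly listed as acceptable.

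A reader might also link poor understanding to the planned 33% refusal of diagnostic assessment (about 100 of 300 screen-positives in section E). The documents do not support this. That rate is a planning figure, declining assessment is a choice open to subjects, and nothing connects it to the consent check.

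Finally, section L notes that people with mild to moderate dementia often have decision-making capacity. The 240 therefore cannot be read as people unable to consent.

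**Conclusion.** The defect is real but limited. As written, the script would score a person who has misunderstood the study as able to consent, and it can be passed without showing awareness of possible dementia screening. This follows from the text alone. It rests on one reasonable reading: that the script is how the inclusion criterion is applied. The protocol does not say so in those words, but it presents the questions as its procedure for addressing capacity.

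How many people are affected is unknown, and the documents give no basis for an estimate. The check belongs to consent, which comes before a subject is allocated, so it does not in itself unbalance the arms. No sample size, power or alpha figure depends on it.

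A reader might go further and call for extra comprehension items with an all-correct rule. The documents do not settle that. Such a rule could draw attention to cognitive testing among the 2,000 controls, against the stated aim in section E (Screening Process). It could also exclude more people with undiagnosed dementia, the subgroup for which section I assumes the 0.40 SD effect. That trade-off belongs to the IRB.

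**What to change.** Delete the friend-or-relative answer from question 1 and replace it with one that fits this trial, for example: *Answer questions about my own health, and I may or may not be given a memory test*. This gives the interviewer a standard that reflects both self-report and the chance of screening. Use the same form for in-person and telephone consent, and bring the in-person statement in section L into line with Telephone Recruitment in section E.

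Whether the generic survey answer should remain enough by itself, whether to add items, and whether all items must be answered correctly can be left to IRB judgement.

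The cost is a small amendment to one form. A few subjects may need a re-explanation before they pass. The example is a scoring aid and need not be read aloud, so it should add little emphasis on cognitive testing.
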